4.2 Subject Exclusion Criteria

1. The subject permanently discontinued study drug during the previous study (TDE-PH-202, TDE-PH-203, TDE-PH-205, TDE-PH-301, TDE-PH-302, or TDE-PH-308) due to treatment related adverse events.
2. The subject permanently discontinued study drug during the Treatment Phase of the previous study (TDE-PH-202, TDE-PH-203, TDE-PH-205, TDE-PH-301, TDE-PH-302, or TDE-PH-308) due to clinical worsening (as defined in those study protocols) and did not undergo premature termination assessments prior to discontinuing study drug, and/or did not complete all remaining study visits through the final scheduled visit.
3. The subject permanently discontinued study drug during the Treatment Phase of the previous study (TDE-PH-301, TDE-PH-302, or TDE-PH-308) due to clinical worsening, completed premature termination assessments prior to discontinuing study drug, completed all remaining scheduled study visits AND received UT-15C SR during the Treatment Phase of the previous study (TDE-PH-301, TDE-PH-302, or TDE-PH-308).

Subjects enrolled in the TDE-PH-202 study who were randomized into the iMTD group who clinically worsen may not participate. Subjects who permanently discontinue study drug during

the 12-week Treatment Phase due to treatment related adverse events are not eligible even if they complete all remaining scheduled study visits. Subjects who permanently discontinue study drug during the 12-week Treatment Phase and do not undergo premature termination assessments prior to discontinuing study drug and/or who do not complete all remaining study visits through the Week 12 visit are also not eligible.

4. The subject must not have developed any concurrent illness or condition during the conduct of the previous study, including but not restricted to, sleep apnea, chronic renal insufficiency, anemia, uncontrolled systemic hypertension or left sided heart disease, unless their physician feels that entry into this study would not be detrimental to their overall health.

5 SUBJECT ENROLLMENT

5.1 Treatment Assignment

All subjects will receive UT-15C SR during the open-label study.

5.2 Randomization

This study is not randomized.

5.3 Blinding

This study is not blinded.

6 DRUGS AND DOSING

6.1 Drug Dosage, Administration and Schedule

UT-15C SR tablets will be provided as 0.25, 0.5, 1, and 2.5 mg tablet strengths. They may also be provided as 0.125 mg strength, if available. The 0.125, 0.25, 0.5, 1, and 2.5 mg tablets are colored blue, green, white, yellow, and pink, respectively.

For subjects who were randomized to placebo in protocols TDE-PH-301, TDE-PH-302, or TDE-PH-308, dosing of UT-15C SR will be initiated and optimized as in the previous protocol, including all safety monitoring including periodic telephone contacts. That is, the first dose of UT-15C SR (0.25 mg) should be taken by the subject immediately following (~ 10 minutes) a meal while at the study site. The subject should remain close to the study site for approximately 3 to 6 hours for periodic observation and monitoring of possible AEs.

Subjects who were randomized to UT-15C SR, or were receiving active therapy in the previous trial will begin open-label therapy at the same dose and regimen (e.g. BID or TID) they were receiving at the final visit in the previous trial, and subsequent dose adjustments will be made based on symptoms of PAH and AEs.

With Amendment 5, subjects may now receive UT-15C either twice (BID) or three (TID) time daily. The decision to transition subjects from BID to TID is up to the discretion of the principal investigator, and not a requirement of the protocol.

The dose of UT-15C SR at the time the subject is discharged from each study visit should be recorded on the CRF.

6.1.1 Twice Daily Dosing Regimen

The next dose of study drug should be taken the following morning. At this time oral dosing of UT-15C SR will be initiated at 0.25 mg twice daily (every 12 hours +/- 1 hour) immediately following (~10 minutes) breakfast and dinner. Subjects must be instructed to take the appropriate amount of 0.25, 0.5, 1, and/or 2.5 mg tablets based upon their given dose. In general, the dose of study drug should be increased in 0.25 to 0.5 mg increments every 3 days, in the absence of dose-limiting drug-related side effects, to ensure the subject receives the optimum clinical dose throughout the study. The 0.125 mg strength, if available, may be used throughout the study if a 0.25 mg dose increase is not tolerated and an intermediate dose is required. Dose changes should be conducted under appropriate medical supervision in consultation with the study site.

6.1.2 Transition from Twice to Three Times daily Dosing

For subjects enrolled in the TDE-PH-304 study who are receiving UT-15C twice daily, dosing frequency may be transitioned from BID to TID. For applicable subjects, it is recommended to reduce the total daily dose administered during BID dosing by approximately 25% and divide the total daily dose into a TID regimen using the appropriate tablet strength(s). Please see Table 6-1 below for examples of transitioning from BID dosing to TID dosing. However, dose modification should occur in accordance with investigator judgment.

Table 6-1 Example Transition from Twice Daily to Three Times Daily Dosing of UT-15C

BID Dosing Regimen	Total Daily Dose with BID Dosing	Total Daily Dose with BID Dosing Reduced by 25%	TID Dosing Regimen	Total Daily Dose with TID Dosing
3 mg BID	6 mg	4.5 mg	1.5 mg TID	4.5 mg
5 mg qAM; 5.25 mg qPM	10.25 mg	7.6875 mg	2.5 mg TID	7.5 mg
6 mg BID	12 mg	9 mg	3 mg TID	9 mg
6.5 mg qAM; 6.625 mg qPM	13.125 mg	9.844 mg	3.25 mg TID	9.75 mg
10 mg BID	20 mg	15 mg	5 mg TID	15 mg
11 mg qAM; 11.5 mg qPM	22.5 mg	16.875 mg	5.5 mg TID	16.5 mg
13 mg BID	26 mg	19.5 mg	6.5 mg TID	19.5 mg
17.125 mg qAM; 17.25 mg qPM	34.375 mg	25.781 mg	8.5 mg TID	25.5 mg

Dose changes should be conducted under appropriate medical supervision in consultation with the study site. If dose titration is considered appropriate, site personnel will instruct the subject to modify their dose; dose changes will be recorded in source documentation and CRF by site personnel.

6.1.3 Three Times (TID) Daily Dosing Regimen

For subjects entering the TDE-PH-304 study receiving a TID dosing regimen (e.g. TDE-PH-205), or for those subjects transitioning from BID to TID dosing, the dosing regimen should be managed as follows:

- TID (every 6-8 hours) with food
- Increases should occur in increments of 0.125 or 0.25 mg TID every 3 days.

In general, the dose of study drug should be increased in 0.125 to 0.25 mg increments every 3 days, in the absence of dose-limiting drug-related side effects, to ensure the subject receives the optimum clinical dose throughout the study. The 0.125 mg strength, if available, may be used throughout the study if a

0.25 mg dose increase is not tolerated and an intermediate dose is required. Dose changes should be conducted under appropriate medical supervision in consultation with the study site.

6.1.4 Dosing of Study Medication in Relation to Meals

Subjects should take study drug approximately every 12 hours (+/- 1 hour) for BID dosing and every 6 – 8 hours for TID dosing, with approximately 240 mL (8 ounces) of water or other beverage (e.g. juice, milk, soda, etc.) immediately after (~ 10 minutes) consuming food (approximately 250 calories).

Subjects should be instructed to be careful not to break, chew, or disrupt the integrity of the tablet as this will result in inappropriate delivery of the active ingredient. If the tablet is inadvertently damaged during administration, the subject should contact site personnel in order to be monitored for the onset of symptoms due to possible overdose.

6.2 Compliance

At each visit, the Investigator or designee will evaluate the amount of UT-15C SR provided to each subject and any returned medication (as required for drug accountability purposes), and compare this accounting with the subject's dosing pattern to obtain an estimate of overall compliance. Each subject will also be asked at each visit whether he or she is in compliance with dosing instructions. If it is determined that a subject is not compliant with study drug then site personnel should re-educate the subject on proper dosing compliance. Continued non-compliance may lead to discontinuation of the subject, after consultation between the Investigator and sponsor.

7 EXPERIMENTAL PROCEDURES

7.1 Open-Label Phase

All values collected at the subject's respective final visit in protocol TDE-PH-202 TDE-PH-203, TDE-PH-205, TDE-PH-301 or TDE-PH-308 and TDE-PH-302 will serve as the baseline assessments for the open-label study.

Subjects receiving placebo in the previous study must be contacted weekly by telephone (at a minimum) during the first 12 weeks of the open-label study and, if necessary, brought in for clinic visits in the first several months of the study to ensure subject safety. This also applies to subjects enrolled from the TDE-PH-202 study (Dose Groups 1 or 2) who are beginning a dose of 0.25mg BID.

Monthly telephone calls (at a minimum) must be conducted for all subjects actively participating in the open-label study, regardless of study drug allocation (UT-15C SR or placebo) in the previous study.

In addition to the scheduled study visits, as listed below, all subjects must be seen in the clinic no less than once every six months for routine standard of care medical evaluation.

Weekly telephone calls (required Weeks 1-12; only for subjects randomized to placebo in previous study). This also applies to subjects enrolled from the TDE-PH-202 study (Dose Groups 1 or 2) who are beginning a dose of 0.25mg BID.

- Adverse events
- PAH concomitant medications
- Concomitant medications

Drug accountability / compliance

Weekly telephone calls (required for 4 weeks for subjects who transition from BID to TID dosing)

- Adverse Events
- PAH concomitant medications
- Concomitant medications
- Drug accountability/compliance

Monthly telephone calls (required for all subjects participating in open-label study)

- Adverse events
- PAH concomitant medications
- Concomitant medications
- Drug accountability / compliance

Visit 1 (three months after first dose of UT-15C SR; only for subjects randomized to placebo in previous study). This also applies to subjects enrolled from the TDE-PH-202 study (Dose Groups 1 or 2) who are beginning a dose of 0.25mg BID.

- Adverse events
- PAH concomitant medications
- Concomitant medications
- Clinical laboratories
- Drug accountability/compliance

Visit 2 (six months after first dose of UT-15C SR)

- Adverse events
- PAH concomitant medications
- Concomitant medications
- Clinical laboratories
- Drug accountability/compliance

Visit 3 (12 months after first dose of UT-15C SR)

- Adverse events
- PAH concomitant medications
- Concomitant medications
- Clinical laboratories
- Drug accountability/compliance
- 6-Minute walk test/borg dyspnea score

Visit 4 (24 months after first dose of UT-15C SR)

- Adverse events
- PAH concomitant medications
- Concomitant medications
- Clinical laboratories
- Drug accountability/compliance

Visit 5 (36 months after first dose of UT-15C SR)

- Adverse events
- PAH concomitant medications
- Concomitant medications
- Clinical laboratories
- Drug accountability/compliance

Yearly visits beyond 36 months

- Adverse events
- PAH concomitant medications
- Concomitant medications
- Clinical laboratories
- Drug accountability/compliance

Exit (premature discontinuation)

- Adverse events
- PAH concomitant medications

- Concomitant medications
- Clinical laboratories
- Drug accountability/compliance

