3 EXPERIMENTAL PLAN

3.1 Study Design

This is an open-label study. Each subject's visit schedule will allow assessments after defined periods of exposure to UT-15C SR (3, 6, 12, 24 and 36 months total exposure). The study will continue with yearly visits beyond 36 months until either UT-15C SR is approved by the appropriate regulatory authorities or the study is discontinued by the sponsor. Therefore, the actual date of each visit will be determined by the date on which the subject first received UT-15C SR (e.g., the date of study drug initiation in TDE-PH-301, TDE-PH-302, or TDE-PH-308 for subjects who were randomized to active therapy in those trials, and the date of UT-15C SR initiation in this study for subjects who were randomized to placebo in the previous controlled trial). Note that the TDE-PH-202, TDE-PH-203, TDE-PH-205 studies are open-label design and therefore will follow the regimen for subjects receiving UT-15C SR.

Subjects enrolled from the TDE-PH-202 study who were in Dose Groups 1 or 2 and permanently discontinued treatment may enter the study if they undergo all premature termination assessments prior to discontinuing study drug and complete all remaining scheduled study visits and assessments (with the exception of the hemodynamic measurements) through Week 12. These subjects should follow the same procedures as subjects who received placebo in the previous study and will begin on a dose of 0.25mg BID.

Subjects randomized to UT-15C SR in Protocol TDE-PH-301, TDE-PH-302, or TDE-PH-308 will complete visits 2-5 and yearly visits thereafter, while subjects randomized to placebo in Protocol TDE-PH-301, TDE-PH-302, or TDE-PH-308 will complete visits 1-5 and yearly visits thereafter. A 6-Minute Walk test and Borg Dyspnea Score will be conducted at the visit occurring 12 months after the subject's initial exposure to UT-15C SR.

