3.2 Overall Schedule of Times and Events

The overall schedule of Time and Events is shown in Table 3.2. Note that the timing of each visit depends upon when the subject first received UT-15C SR (e.g. whether the subject was assigned to active or placebo treatment in Protocol TDE-PH-301, TDE-PH-302, or TDE-PH-308). Subjects receiving placebo in the previous study, or subjects enrolled from the TDE-PH-202 study who are beginning a dose of 0.25mg BID, must be contacted weekly by telephone (at a minimum) during the first 12 weeks of the open-label study to ensure subject safety. More specifically, these calls should assess study drug dose titration needs, potential adverse events, concomitant medication usage and PAH signs and symptoms. Monthly telephone calls (at a minimum) must be conducted for all subjects actively participating in TDE-PH-304, regardless of study drug allocation (UT-15C SR or placebo) in the previous study, to assess dose titration needs, potential adverse events, concomitant medication usage and PAH signs and symptoms. In addition to the scheduled study visits, all subjects must be seen in the clinic no less than once every six months for routine standard of care medical evaluation.

Subjects enrolling from the TDE-PH-203 and TDE-PH-205 studies will transition on the same dose they were receiving at the end of the study. Study visits for the TDE-PH-304 protocol will be based on the date the subject first received active UT-15C in their respective preceding study.

Table 3.2. Time and Events

Assessment	Visit ^{4,5,6,7}						
	Visit 0-1 (Weeks 1-12) ³	1	2	3	4	5+ ⁸	EXIT ⁹
Adverse Events	X	X	X	X	X	X	X
PAH Concomitant Medications	X	X	X	X	X	X	X
Concomitant Medications	X	X	X	X	X	X	X
6-Minute Walk Test/Borg Dyspnea Score ¹				X			
Clinical Laboratory Parameters ²		X	X	X	X	X	X
Drug Accountability/Compliance	X	X	X	X	X	X	X

¹ **6-Minute Walk Test/Borg Dyspnea Score** as described in Appendix A. conducted 3 to 6 hours after the morning dose of UT-15C SR.

² **Laboratories** to be collected are described in Appendix B.

³ **Weekly telephone calls** (at a minimum) required during Weeks 1-12 for subjects randomized to placebo in TDE-PH-301, 302, or 308 to assess dose titration needs, potential adverse events, concomitant medication usage and PAH signs and symptoms. Also applies to subjects enrolled from the TDE-PH-202 study who are beginning a dose of 0.25mg BID.

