⁴ **Visit windows** are ± 1 month from the scheduled number of months from first exposure to UT-15C SR, except for Visit 1, which is ± 2 weeks.

⁵ **VISIT 1** – Only for subjects randomized to placebo in TDE-PH-301, 302, or 308; 3 months after subject's first exposure to UT-15C. Also applies to subjects enrolled from the TDE-PH-202 study who are beginning a dose of 0.25mg BID.

VISIT 2 – 6 months after subject's first exposure to UT-15C SR.

VISIT 3 – 12 months after subject's first exposure to UT-15C SR.

VISIT 4 – 24 months after subject's first exposure to UT-15C SR.

VISIT 5 – 36 months after subject's first exposure to UT-15C SR.

⁶ **Weekly telephone call** required for 4 weeks for all subjects who transition from a BID to TID regimen to assess dose titration needs, potential adverse events, concomitant medication usage and PAH signs and symptoms.

⁷ **Monthly telephone calls** (at a minimum) required for all subjects participating in TDE-PH-304 to assess dose titration needs, potential adverse events, concomitant medication usage and PAH signs and symptoms.

⁸ **Visits beyond Visit 5** will occur yearly until either the drug receives regulatory approval in a particular region or the sponsor discontinues the study. Assessments after visit 5 will include adverse events, PAH concomitant medications, concomitant medications, clinical laboratories, and compliance/drug accountability.

⁹ **EXIT** – If the subject discontinues from the study between scheduled visits, every effort should be made to obtain the exit assessments just prior to termination from the study.

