3.3 Clinical Assessments

3.3.1 Efficacy

A 6-Minute Walk Test with Borg Dyspnea Score (described in Appendix A) will be conducted at Visit 3, 12 months from the subject's first exposure to UT-15C SR. The 6-Minute Walk Test should be conducted approximately 3 to 6 hours after the morning dose of UT-15C SR.

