3.5 Number of Subjects

Approximately 900 subjects will be enrolled across all sites participating in either TDE-PH-202, TDE-PH-203, TDE-PH-205, TDE-PH-301, TDE-PH-302, or TDE-PH-308. Additional subjects may be enrolled from other clinical protocols evaluating UT-15C SR in subjects with PAH. All subjects successfully completing all assessments in either protocol TDE-PH-202, TDE-PH-203, TDE-PH-205, TDE-PH-301, TDE-PH-302, TDE-PH-308 or other UT-15C SR clinical protocols are eligible for participation.

Subjects randomized into Dose Group 1 or Dose Group 2 in the TDE-PH-202 study who permanently discontinue study drug during the 12-week Treatment Phase due to clinical worsening are eligible for entry into the TDE-PH-304 if they undergo all premature termination assessments prior to discontinuing study drug and complete all remaining scheduled study visits and assessments (with the exception of the hemodynamic measurements) through Week 12. Such subjects should start treatment with UT-15C in the open-label study at 0.25 mg BID.

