10 DATA MANGEMENT AND STATISTICS

Completed CRFs will be forwarded to United Therapeutics or its designee for processing. A quality-assured computerized database will be constructed. Data will be listed and also will be summarized either in tabular and/or graphical presentations.

The safety of UT-15C SR will be assessed using laboratory assessments and reports of adverse events. All reported adverse events will be assigned MedDRA terms which will be listed and summarized according to intensity, seriousness and causality.

Efficacy assessments (6-Minute Walk/Borg Dyspnea Score) may be compared to assessments in Protocols TDE-PH-202, TDE-PH-203, TDE-PH-205, TDE-PH-301, TDE-PH-302, TDE-PH-308, or TDE-PH-304, as appropriate. Doses of UT-15C SR will be listed, summarized and analyzed for trends over time.

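### Baseline is fixed at the final parent-study visit while Month 12 runs from first UT-15C SR dose, so the Month-12 walk and Borg changes measure different things in ex-placebo and ex-active subjects

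*Protocol*

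**What the plan says.** **Baseline.** Protocol 7.1 takes all values at the final visit of the six named parent protocols and states that they "will serve as the baseline assessments for the open-label study". It makes no distinction between subjects who were on active drug and those on placebo. It is the only text in either document that names a baseline visit.

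**Time origin.** Protocol 3.1 says that "the actual date of each visit will be determined by the date on which the subject first received UT-15C SR": study drug start in the parent trial for subjects randomized to active, and UT-15C SR start in TDE-PH-304 for those randomized to placebo. The open-label 200-series studies follow the active pattern. Under Protocol 3.3.1 the walk test with Borg score "will be conducted at Visit 3, 12 months from" first exposure. Table 3.2, footnote 4, sets a window of ±1 month "from the scheduled number of months from first exposure to UT-15C SR".

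**Analysis.** SAP 10.1 summarises baseline, Month-12 and change values for walk distance and Borg score. Baseline is also used for WHO functional class (SAP 9.3.2) and for laboratory shifts (SAP 11.5). The SAP does not define it. SAP Section 7 includes parent-study data for ex-active subjects and restricts ex-placebo subjects to their baseline data, but names no visit. Protocol Section 10 leaves the comparator open: "Efficacy assessments (6-Minute Walk/Borg Dyspnea Score) may be compared to assessments in Protocols" of the parent studies or of TDE-PH-304, as appropriate.

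**Restarters.** TDE-PH-202 Dose Group 1 or 2 subjects "who permanently discontinue study drug during the 12-week Treatment Phase due to clinical worsening" may enter and restart. Protocol 3.1 says "These subjects should follow the same procedures as subjects who received placebo in the previous study", and Protocol 3.2 says they "must be contacted weekly by telephone (at a minimum) during the first 12 weeks of the open-label study".

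**The concern.** The third study objective is the effect of continued therapy on exercise capacity at one year of treatment. With baseline at rollover and Month 12 at one year from first dose, two different quantities result. For ex-placebo subjects the change runs over about a year from a value taken before any UT-15C SR. For continuing ex-active subjects it starts from a value taken on drug, and whatever happened during the parent treatment period falls before baseline and is not counted.

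The two quantities would be averaged in:

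- the overall row;
- the pooled TDE-PH-301/308 row and the TDE-PH-302 row;
- the subgroup rows not split by prior assignment (PAH medication use, etiology, WHO class, dosing quartiles and tertiles).

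The 200-series row is not mixed in this way, apart from restarters and possibly the two de novo TDE-PH-301 subjects. Tables 14.2.1.3 and 14.2.1.4 do separate prior active from prior placebo, but part of any difference they show would come from the baseline rule. The split of subjects by baseline walk at 380 m (Table 14.2.1.11) and the laboratory shift plots depend on the same undefined term.

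**Working it through.** The plan states no figure to reproduce: the sample size is an enrolment assumption (SAP Section 6). The check is date arithmetic.

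**Inputs**

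- Baseline: final parent-study visit (Protocol 7.1).
- Month 12: 12 months from first UT-15C SR dose, ±1 month (Protocol 3.3.1; Table 3.2, footnote 4).
- Continuing ex-active subjects are on drug at rollover, because they carry over the dose of their final parent visit (Protocol 6.1).
- TDE-PH-202 treatment phase: 12 weeks (Protocol 3.5). No length is given for TDE-PH-203, 301, 302 or 308. TDE-PH-205 is excluded from the walk and Borg summaries (SAP 10.1).
- 1 month = 365.25 / 12 = 30.44 days.

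**Formula.** Let d be the months on active drug at the final parent visit. The interval from baseline to Month 12 is 12 − d, with windowed range (11 − d) to (13 − d).

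**Ex-placebo.** d = 0, so 12 months (11 to 13), taking the first open-label dose to be at or close to the final parent visit.

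**TDE-PH-202 completers.** d = 84 / 30.44 = 2.76 months. Interval = 12 − 2.76 = 9.24 months; 1 − 9.24/12 = 23% shorter. Windowed range: 8.24 to 10.24 months, which does not meet 11 to 13.

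**Other parent studies.** The ranges separate once 13 − d < 11, that is d > 2 months (60.9 days, 8.7 weeks). The lengths below are assumptions for illustration, not values from the documents.

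| Assumed time on active drug | Interval (months) | With window |
|---|---|---|
| 8 weeks | 10.2 | 9.2-11.2 |
| 16 weeks | 8.3 | 7.3-9.3 |
| 24 weeks | 6.5 | 5.5-7.5 |

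**Restarters.** Placebo-type procedures, with weekly calls in Weeks 1-12 and then Visit 1 at 3 months, point to counting from restart. Counted from the first TDE-PH-202 dose, Visit 1 would fall at 3 × 30.44 = 91 days, about a week after the Week 12 parent visit. Yet the first-exposure wording of the footnotes to Table 3.2 is not adapted for them. If baseline and Month 12 are both anchored to restart, the interval is about 12 months. If baseline precedes the first TDE-PH-202 dose and Month 12 counts from a restart at Week 12 or later, it is at least 12 + 2.76 = 14.8 months.

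**De novo subjects.** For the two subjects withdrawn from TDE-PH-301 and enrolled directly (SAP Section 8), neither a baseline visit nor any earlier active exposure is stated.

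**What the SAP seems to intend.** Age and years since diagnosis are computed at first active dose (SAP 9.3.1, 9.3.2). Clinical events, exposure and treatment-emergent events reach back into the parent study for ex-active subjects (SAP 10.2, 11.1, 11.2). TDE-PH-205 is left out because no gain was expected after transition. All this fits a baseline before first active dose, but the SAP does not say so, and that reading contradicts Protocol 7.1.

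**Laboratory data.** SAP 11.5 takes in all parent-study values, while SAP Section 7 admits only baseline values for ex-placebo subjects. SAP 11.5 also does not limit the plotted minimum and maximum to values after baseline. Under Protocol 7.1, on-drug parent-study values from before baseline could therefore be plotted as shifts from it.

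**The case against.** The strongest reply is that Protocol 7.1 is a procedural statement explaining why there is no separate entry visit, and that the SAP, which supplies the analysis detail, points to a pre-first-dose baseline. On that reading the mixing disappears. But the SAP never states it, and the only stated rule says otherwise. A programmer must either follow the protocol or guess.

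Several limits do stand:

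- The one interval that the documents fix (9.2 against 12 months) compares TDE-PH-202 completers with ex-placebo subjects from other studies, so it shows in the overall and subgroup rows. For the TDE-PH-301/308 and 302 rows no value can be given.
- The 14.8-month restarter figure does not arise from Protocol 7.1. It arises only if baseline is moved before the first parent dose without moving Month 12 too, so the remedy has to cover this group.
- Month-12 absolute values and the 380 m achievement table (14.2.1.10) do not depend on baseline.
- Change from rollover is a legitimate description of continued therapy, provided that it is labelled as such.
- The two de novo subjects are a tiny share of about 900.

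**Conclusion.** Wrong as written, and it should be fixed. The stated baseline rule and the stated time origin together give a Month-12 change that is not a one-year change for continuing ex-active subjects, and that is not comparable with the ex-placebo change. For TDE-PH-202 completers the interval is 9.2 months, 23% short, with non-overlapping windows. For TDE-PH-203, 301, 302 and 308 it is 12 − d, with d unknown. No effect in metres can be derived from the documents.

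The conclusion rests on following Protocol 7.1 literally, on the final TDE-PH-202 visit falling at Week 12, and on ex-placebo subjects starting drug at about their final parent visit. The rule covers the six named parent protocols; subjects from additional protocols have no stated baseline at all. Because the analysis is descriptive with no power calculation, the harm is to interpretation and not to error control.

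**What to change.** 1. In SAP Section 8, define baseline for walk distance, Borg score, WHO class and laboratory shifts as the last non-missing value before the first dose of active UT-15C SR. This gives both groups an interval of about 12 months (11 to 13 with the window) from an off-drug value.
2. State there that this departs from Protocol 7.1, and reconcile the protocol wording at the next amendment.
3. Specify the analysis baseline and first-exposure date for TDE-PH-202 Dose Group 1/2 restarters and for the two de novo TDE-PH-301 subjects, with baseline and Month 12 tied to the same date.
4. In SAP 11.5, restrict the plotted minimum and maximum to values after that baseline, and reconcile the inclusion of all parent-study laboratory data with the baseline-only limit in SAP Section 7.
5. Optionally, report change since rollover for ex-active subjects in a separately labelled summary.

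The cost is one definition, one plotting restriction and a little table work; SAP Section 7 already brings in parent-study data for ex-active subjects. A protocol change needs regulatory and ethics approval (Protocol 13.1) across about 118 centers, so the two documents will differ, openly, until the next amendment. The reported mean change may differ from the one planned. If earlier interim outputs (SAP Section 5) used another baseline, the change should be footnoted or those tables re-run.
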